**Inclusion criteria**

- i) Histological confirmation of Barrett's esophagus without dysplasia or cancer aged  $\geq 18$  years with  $BMI \geq 25.0 \text{ kg/m}^2$
- ii) Willingness and ability to perform supervised Nordic walking session twice a month and self-planned physical activity at least 3 times a week
- iii) Signed informed consent

## Exclusion criteria

- i) No histological confirmation of Barrett's esophagus
- ii) Cancer diagnosis within one year before trial begins
- iii) Presence of insulin-dependent diabetes
- iv) Denied informed consent

### *-Sample size*

The sample size is based on the primary outcome of a clinically significant change in body weight at the end of the study. A 7% weight loss has been shown to be clinically effective in reducing the risk of diabetes. According to previous data,[44] it is expected that around 30% of patients enrolled in the IA and 15% of those enrolled in the CA will achieve the aforementioned weight loss within the time allotted for trial. In order to reveal a statistically significant difference in the rates of achievement of a 7% weight loss between IA and CA, at least 95 patients are required for each group (power: 80%, type-1 error: 5%). In order to achieve this sample size, we estimate that a pool of 340 patients will be required for recruitment, to allow a recruitment rate of 70% (n=238), and a subsequent drop-out rate of 20% (n=190).

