## OBJECTIVES

In this study, patients are randomly divided into two arms, a control arm and an interventional arm. The aim of this two-arms randomized clinical trial is to assess the effect of a moderate CALoric-protein REstriction PROgram (CARE-PRO) on metabolic-hormonal condition (such as excessive BMI and/or waist circumference (WC), insulin resistance, unbalanced esophageal microbiota composition, chronic inflammation and adipose tissue-related hormones release) which can represent, when altered, a risk factor for the development of esophageal adenocarcinoma in patients with Barrett's esophagus. The control arm receives information about a correct lifestyle

and suggestions to increase the consumption of fiber and vegetable proteins. The interventional arm instead is involved in the two-year program of moderate caloric and protein restriction.

*-Overall aim of the study*

The main objective of the study is to evaluate the impact of a lifestyle-oriented (diet, physical activity, behavior change) intervention on body weight, waist circumference, biomarkers associated with cancer risk, esophageal microbiota composition and adherence to cancer prevention recommendations (WCRF/ARICR 2007) after 24 months in overweight or obese ( $BMI \geq 25.0 \text{ Kg/m}^2$ ) BE patients.

*-Primary aim*

To examine the effect of a dietary and exercise intervention on body weight and waist circumference reduction in overweight or obese BE patients.

*-Secondary aims*

To assess the impact of CARE-PRO intervention on the relationship between anthropometric parameters (body weight, BMI and WC), metabolic serum biomarkers, the expression of proteins involved on insulin and IGF1 receptors signal transduction and esophageal microbiota composition associated with an increased risk of developing EAC.

- i) To assess the impact of CARE-PRO intervention on the adherence to WCRF/AICR recommendations for cancer prevention.[6,38] Adherence to cancer prevention recommendations will be assessed by a validated score of adherence.[39]
- ii) To evaluate possible differences on CARE-PRO outcomes between elderly ( $> 65$  years) BE patients and younger BE patients ( $<65$  years).
- iii) To evaluate economic costs of the intervention.

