### *-Trial design*

The study will be a two-arm, randomized control trial comparing CARE-PRO intervention with usual clinical approach to BE patients. Study enrollment was started in 2015 and will be complete at the end of 2018. The intervention will last 2 years (24 months) and will be accompanied by the normal follow up procedures.[59]

The study team, including research nurses, will be blinded to the patient group allocation until completion of the primary outcome analysis. Only the principal investigator, study administrator, dietitian and participants will not be blinded considering the nature of the intervention. None of these unblinded staff will have a role in data analysis.

Details of the collected outcomes at different time points are showed in Figure xx.

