## Statistical analysis

Fisher's exact test will be used for comparison of categorical variables. Numerical variables will be expressed as median and interquartile range (Q1; Q3). The Mann-Whitney *U*-test will be used to evaluate differences between IA and CA groups. Paired Student's T test will be used to compare the difference in the parameters measured at baseline (at the time of enrolment) and at the end of the trial in the same patient. Spearman's rank correlation coefficient will be calculated to evaluate the correlation between two measured parameters. All tests will be two-tailed and a *p* value lower than 0.05 will be assumed to indicate a significant difference. Data analyses will be performed with SPSS v20 and Stats-Direct.

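### The planned 95 patients per group give about 65% power for 30% versus 15% under the plan's two-tailed Fisher's exact test, not the stated 80%

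*Combined protocol and SAP*

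**What the plan says.** The Sample size section bases the calculation on achieving a 7% weight loss by the end of the study. It expects that "around 30% of patients enrolled in the IA and 15% of those enrolled in the CA will achieve the aforementioned weight loss", and concludes that "at least 95 patients are required for each group (power: 80%, type-1 error: 5"%). It gives no formula, test or sidedness. It then works back to recruitment: a pool of 340, of whom 70% (238) are recruited, followed by "a subsequent drop-out rate of 20% (n=190"). The 190 are two groups of 95, so 95 is the number expected to be evaluable, not the number randomised.

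The Statistical analysis section states "Fisher's exact test will be used for comparison of categorical variables" and "All tests will be two-tailed", with significance at p below 0.05. Reaching or not reaching a 7% loss is a categorical variable, so these rules govern the comparison on which the trial was sized.

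The Objectives section words the primary aim differently, as an effect "on body weight and waist circumference reduction in overweight or obese BE patients", without a threshold. No power is stated for a continuous analysis of weight or waist.

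**The concern.** The sample-size paragraph and the analysis section do not describe the same test. For 30% versus 15%, 95 per group is lower than a two-sided 5% test needs for 80% power, and Fisher's exact test is more conservative again.

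This is the only power statement in the plan, and readers will use it to judge a non-significant result. If they believe the trial had an 80% chance of detecting a doubling of the response rate, they will read a null responder comparison as stronger evidence against the programme than it is.

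**Working it through.** **Inputs.** From the Sample size section: p₁ = 0.30, p₂ = 0.15, power 0.80, type-1 error 0.05, 95 per group, recruitment 70%, drop-out 20%. From the Statistical analysis section: two-tailed, Fisher's exact test. Equal allocation is implied by the equal group sizes.

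**1. Reproducing 95.** The usual two-proportion formula, with p̄ = (0.30 + 0.15)/2 = 0.225, is

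n = [z_α √(2p̄(1−p̄)) + z_β √(p₁(1−p₁) + p₂(1−p₂))]² / (p₁−p₂)²

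- √(2 × 0.225 × 0.775) = 0.5906
- √(0.21 + 0.1275) = 0.5809
- z_β = 0.8416
- (p₁−p₂)² = 0.0225

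One-sided 5% (z_α = 1.6449): (0.9714 + 0.4889)² / 0.0225 = **94.8, i.e. 95**, which is the plan's figure.

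Two-sided 5% (z_α = 1.9600): (1.1575 + 0.4889)² / 0.0225 = **120.5, i.e. 121**.

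Other two-sided versions also miss 95: unpooled variance 118, arcsine 119, continuity-corrected 134.

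**2. Power at 95 per group, normal approximation.** Power = Φ[((p₁−p₂)√n − z_α × 0.5906)/0.5809], with 0.15 × √95 = 1.4620.

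- One-sided: Φ[(1.4620 − 0.9714)/0.5809] = Φ(0.845) = 80.1%
- Two-sided: Φ[(1.4620 − 1.1575)/0.5809] = Φ(0.524) = 70.0%

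**3. Exact power.** All 96 × 96 possible outcomes at 95 per group were enumerated. The binomial probabilities were summed over outcomes with two-sided p < 0.05.

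| Analysed per group | True rates | Fisher | Uncorrected chi-square |
|---|---|---|---|
| 95 | 30% vs 15% | 64.9% | 70.7% |
| 119 (all 238, no loss) | 30% vs 15% | 75.8% | 80.2% |
| 119 (drop-outs as non-responders) | 24% vs 12% | 62.2% | 68.6% |

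The last row takes 30% and 15% as rates among completers: 0.30 × 0.8 = 0.24 and 0.15 × 0.8 = 0.12. Of the 15-point shortfall in the first row, sidedness accounts for about 10 points (80.1% to 70.0%) and Fisher's conservatism for about 5.

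**4. What 80% would take.** Two-sided Fisher first reaches 80% at 131 per group (80.1%; 130 gives 79.7%). With the control rate held at 15%, 95 per group give 80% power for an intervention rate of about 33.1% (Fisher) or 32.0% (chi-square).

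**5. Drop-out arithmetic.** 340 × 0.70 = 238, and 238 × 0.80 = 190.4, so the chain is consistent. It delivers 95 evaluable per group and no more.

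**The case against.** The plan never says that its calculation was one-sided. That is an inference from the match at 95, and another tool or a slip could have produced the figure. This is fair, but the shortfall does not depend on the origin: however 95 was reached, it does not give 80% power under the stated analysis.

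The analysis section assigns Fisher's exact test to categorical variables in general and does not name the responder comparison. The primary aim could also be read as continuous, with the Mann-Whitney test between arms. This limits the point to the 7% responder comparison. It does not remove it, because that comparison is the stated basis of the sample size, and even the uncorrected chi-square test falls about 9 points short.

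The inputs are soft, since the plan says around 30%. At 95 per group, 32% versus 15% gives 75.3% with Fisher and 80.1% with chi-square. But 28% versus 15% gives 53.1% with Fisher, so the uncertainty cuts both ways, and a power statement has to follow from its own inputs.

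The strongest reply concerns the denominator, because no analysis set or missing-data rule is given. If all 238 patients had outcomes at undiluted rates, chi-square power would be 80.2%. That requires no drop-out, contrary to the plan's 20%, and a test the plan does not name. Fisher would still give 75.8%.

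Finally, the plan says "Study enrollment was started in 2015 and will be complete at the end of 2018", so a larger trial may not be practical. That bears on which remedy to choose, not on whether the statement is wrong.

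**Conclusion.** The concern holds. For 30% versus 15% with 95 evaluable per group at two-sided 5%, power is about 65% with the planned Fisher's exact test and about 71% with an uncorrected chi-square test. The chance of missing the planned effect is therefore about 35% or 29%, against the 20% implied. Planned Fisher power stays below 80% under each denominator examined.

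This rests on the plan's response rates, equal groups, and the responder outcome being analysed as the Statistical analysis section prescribes for categorical variables. It says nothing about power for continuous weight or waist. It must be corrected because the plan's only power claim is not met by its own analysis.

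**What to change.** Restate the Sample size paragraph along these lines: *95 evaluable patients per group give about 65% power (two-sided Fisher's exact test, 5% level) to detect 30% versus 15%; power is 80% for about 33% versus 15%.* Naming the test and its sidedness there brings the paragraph into line with the Statistical analysis section. The cost is a few sentences and a less favourable stated power. No patients, tests or data change.

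If 80% power for 30% versus 15% is to be kept, the paragraph must carry the numbers that requires at 20% drop-out:

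- **Fisher, 131 per group:** 262/0.8 = 327.5, so 328 randomised, from a pool of 328/0.7 = 469.
- **Uncorrected chi-square, 121 per group by the approximate formula:** 242/0.8 = 302.5, so 303 randomised, from a pool of 303/0.7 = 433. By exact enumeration 119 per group suffices (238/0.8 = 297.5, so 298 randomised). This route also means changing the named test.

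Using the 303 and 328 figures, that is 65 to 90 more randomised patients than the planned 238, which the 2018 close of enrolment may rule out.

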### *-Trial design*

The study will be a two-arm, randomized control trial comparing CARE-PRO intervention with usual clinical approach to BE patients. Study enrollment was started in 2015 and will be complete at the end of 2018. The intervention will last 2 years (24 months) and will be accompanied by the normal follow up procedures.[59]

The study team, including research nurses, will be blinded to the patient group allocation until completion of the primary outcome analysis. Only the principal investigator, study administrator, dietitian and participants will not be blinded considering the nature of the intervention. None of these unblinded staff will have a role in data analysis.

Details of the collected outcomes at different time points are showed in Figure xx.

### *-Randomization*

At the time of enrollment, prior to group allocation, anthropometric and body composition measurements (such as height, body weight, waist circumference at the umbilical level, BMI [weight/(height) (Kg/m^2) will be recorded for each patient immediately before endoscopic procedure. Patients will be randomly allocated by a data manager in the intervention (IA) or control arm (CA), using a permuted-block technique, with block size of four or eight. The Data Manager will not be involved in recruitment or intervention process.

### *-Blood and biopsy sample collection*

Immediately before endoscopy, blood samples will be obtained from each patient (after 10-12 hours fasting) and blood glucose will be determined with a glucometer (Abbott Laboratories®, TX, USA). Serum will be extracted, aliquoted and frozen in liquid nitrogen. During endoscopy, 4 quadratic esophageal biopsies – according to the Levine protocol – will be obtained, fixed in formalin and sent to the Medicine, Surgical Pathology & Cytopathology Unit for histological examination designed to confirm the presence of Barrett's Esophagus and the evaluation of the presence or absence of dysplasia cancer. Additional target biopsies will be obtained from areas affected by Barrett's Esophagus and frozen in liquid nitrogen.

### *-Serum analysis*

Serum metabolic biomarkers such as fasting glucose (mg/dl) insulin (pg/ml), C-peptide (pg/ml), IGF1 (nmol/ml) and its binding proteins IGFBP1 (nmol/ml) and IGFBP3 (nmol/ml), leptin (ng/ml), adiponectin (μg/ml), TNF-alpha (pg/ml) and IL-6 (pg/ml) levels will be measured in each serum sample with Luminex xMAP® technology (multiplexed fluorescent bead-based immunoassay, Luminex, TX, USA); insulin resistance index (HOMA-IR index) will be calculated using the formula: [fasting plasma glucose (mg/dl) × fasting serum insulin(μU/ml)/405], according to the method developed by Matthews et al.[60] HOMA-IR index  $\geq 2.5$  will be selected as cut-off for insulin-resistance according to Capasso et al.[61]

### *-Esophageal biopsy analysis: Insulin/IGF1 signal transduction and microbiota composition*

Total proteins will be extracted from fresh frozen esophageal biopsy and will be quantified by Bicinchoninic Acid (BCA) assay (Thermo Scientific Pierce, IL, USA). For each sample, 12.5 μg of total proteins will be analyzed to evaluate the activation state of Insulin Receptor (IR) and IGF1 Receptor (IGF1R) signal pathways using Luminex xMAP® technology. Both the metabolic PI3K/Akt pathway and the mitogenic (ERK/MAPK) pathway will be analyzed.

To assess esophageal microbiota profiling, total gDNA will be extracted from fresh frozen biopsy. Specific primers for the bacterial V3-V4 hypervariable regions of 16S rRNA will be used to amplify bacterial DNA [ $\approx$  500 bases pair (bp)] to be sequenced by Illumina MiSeq platform with 300 bp paired-end approach. BMR Genomics (Padua, Italy) will perform the sequencing.

Biopsy and serum samples stored in nitrogen will, as a routine, be managed by the Biological Bank staff who will provide for their conservation in a totally anonymity (as prescribed by law and already authorized by the Ethics Committee with prot. No. P 480 2002)

The acceptance or rejection by patients to participate in the study will not change in any way their established diagnostic-therapeutic procedures and follow-up.

### *-WCRF/AICR adherence score calculation*

In order to determine a score of adherence to cancer prevention recommendations, participants will be asked to complete a self-administrated questionnaire reflecting six out of eight WCRF/AICR recommendations: 1) body fatness; 2) physical activity; 3) energy dense food and drink consumption; 4) plant food consumption; 5) red and processed meat consumption; 6) alcohol intake.

Some recommendations have several sub-recommendations. To each item of the questionnaire, a score of 1 will be assigned when the recommendation is met and a score of 0 will be assigned when it is not. An answer that partially satisfies the recommendation will be assigned a score of 0.5. The final score will derive from the mathematical sum of the individual scores obtained for each recommendation. The maximum expected score will be equal to 6.

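### The adherence score, as written, takes body fatness from unblinded participants' own questionnaire and includes a weight component that overlaps the primary aim; score it from recorded measurements and show the score without it as well.

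*Combined protocol and SAP*

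**What the plan says.** The section on calculating the WCRF/AICR adherence score states that "participants will be asked to complete a self-administrated questionnaire reflecting six out of eight WCRF/AICR recommendations: 1) body fatness"; the other five are physical activity, energy-dense food and drink, plant food, red and processed meat, and alcohol. On scoring it says "To each item of the questionnaire, a score of 1 will be assigned when the recommendation is met", with 0 for not met and 0.5 for partly met. It adds "Some recommendations have several sub-recommendations". The final score is the sum over recommendations, and "The maximum expected score will be equal to 6".

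Under Objectives, secondary aim i is "To assess the impact of CARE-PRO intervention on the adherence to WCRF/AICR recommendations for cancer prevention", and "Adherence to cancer prevention recommendations will be assessed by a validated score of adherence". The primary aim is "To examine the effect of a dietary and exercise intervention on body weight and waist circumference reduction in overweight or obese BE patients".

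The Trial design section says "Only the principal investigator, study administrator, dietitian and participants will not be blinded considering the nature of the intervention". The Randomization section has height, weight, waist and BMI recorded before allocation. The Abstract says that measurements are taken again two years after enrolment.

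**The concern.** There are two linked issues.

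The first is the source of the data. Read literally, all six components, body fatness included, come from a form that the patient fills in. One arm has spent two years being coached to reduce weight, and every patient knows their arm. Any tendency to report a more favourable weight could then differ between arms. The trial already holds recorded values for the same quantity, but the scoring section does not refer to them.

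The second is overlap. Body fatness is counted inside the score, and body weight and waist are the primary aim. A higher total in the intervention arm could come partly or wholly from weight loss. A reader who takes the adherence result as separate evidence that diet and activity changed would be reading part of the weight result a second time. The same applies to correlations: the Statistical analysis section plans Spearman coefficients between measured parameters without naming the pairs. If the score were paired with weight or BMI, part of the correlation would be there by construction.

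**Working it through.** **Weight of the component in the score.** The plan's own maximum is reproduced by allowing one point per recommendation: 6 × 1 = 6. Body fatness is therefore 1/6 = 16.7% of the scale, and a half-point step is 0.5/6 = 8.3%. Without it the maximum is 5.

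**Source of the component.** Set side by side, the sections say three things:
- The score comes from a self-administered questionnaire, with body fatness listed first (adherence score section).
- Respondents are unblinded (Trial design).
- BMI and waist are recorded at enrolment (Randomization), and measurements are repeated at two years (Abstract). Weight at the end of the study is in any case needed for the outcome behind the sample size.

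Nothing links the third statement to the first.

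**Size of the weight-only contribution.** Taken from the documents: 30% and 15% of patients reaching a 7% loss (Sample size), and BMI of at least 25 at entry (Inclusion criteria). The body-fatness cut-points, the baseline BMI distribution and the spread of weight change are not given, so the following are assumptions: 1, 0.5 and 0 points for BMI below 25, 25 to below 30, and 30 or more; baseline BMI normal with mean 29 and SD 4, truncated below at 25.

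1. *Crude figure.* If every patient with a 7% loss gained a half or a whole point and nobody else changed, the arm difference would be 0.5 × (0.30 − 0.15) = 0.075 to 1 × 0.15 = 0.15.
2. *Only those near a cut-point gain.* A 7% loss crosses 25 only from a BMI below 25/0.93 = 26.9, and crosses 30 only from a BMI below 30/0.93 = 32.3. A whole point from a BMI of 30 needs a loss of more than 1 − 25/30 = 16.7%, so a 7% loss earns at most half a point. Share of patients from 25 to 26.9: (0.298 − 0.159)/0.841 = 0.166. Share from 30 to 32.3: (0.792 − 0.599)/0.841 = 0.230. Together 0.396. Arm difference if only responders change, each by 7%: 0.396 × 0.5 × 0.15 = 0.030. With responders' losses spread evenly over 7 to 10% it is 0.036.
3. *Everyone's weight varies.* Here percentage weight change is normal in each arm, with the mean set so that 30% and 15% reach a 7% loss. By simulation, the arm difference in the body-fatness component is:

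| SD of weight change | Arm difference (points) |
|---|---|
| 3% | 0.043 |
| 5% | 0.065 |
| 6% | 0.074 |
| 8% | 0.091 |

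The range is thus about 0.03 to 0.09 points, or 0.03/6 = 0.5% to 0.09/6 = 1.5% of the scale. Error from self-report is not included, because the documents give no figure for its size or direction.

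**The case against.** **The construct.** Secondary aim i concerns adherence to the WCRF/AICR recommendations, and the plan lists body fatness as one of them. A patient who moves into the recommended range has become more adherent as the plan defines it. The plan also calls the score validated, and replacing it with a shortened version would give that up. This stands: the six-component score should remain the measure for aim i. It does not show that a difference in that score reflects behaviour, and a supplementary score costs nothing in validity.

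**The source.** The text does not rule out that the recorded BMI and waist are used. This also stands in part. The supportable statement is that the plan, as written, points to the questionnaire and names no other source, not that self-reported weight will certainly be used.

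**Two stronger readings that the documents do not support.** A reader might infer that the scoring contradicts the maximum of 6, because each item scores up to 1 and some recommendations have sub-items. But the final score sums the scores for each recommendation, and six of those give exactly 6. What is missing is only the rule for reducing sub-items to one score. The plan cites a source for the score, which is not available here and may or may not supply that rule.

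A reader might also infer an inflated false-positive rate. Simulation under assumptions of the kind above, with 95 per arm, no arm difference in the other five components and an SD of 0.8 to 1.0 for their change, gives rejection rates of roughly 7 to 12%. In that setting the arms truly differ on one component of the score, so this is low power to detect a real difference, not type I error.

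**Conclusion.** The point holds as a minor one on a secondary aim. As written, the body-fatness component comes from unblinded participants although recorded values should be available, and weight loss alone can raise the score by up to 1 of 6 points. The expected contribution to the difference between arms is small, roughly 0.03 to 0.09 points. That range depends on the assumed cut-points, baseline BMI distribution and spread of weight change, and could shift if the actual scoring differs. The overlap and the unstated source follow from the text alone and do not depend on those assumptions. The primary outcome and the sample size do not depend on this score.

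**What to change.** In the adherence score section:
- State that body fatness is scored from the BMI and waist recorded at baseline and 24 months, not from the questionnaire answer, and give the cut-points.
- Keep the full six-component score as the measure for secondary aim i.
- Report beside it, as a supplementary analysis, the five-component score without body fatness (maximum 5). Use that version for any statement about behaviour change and for any correlation with weight, BMI or waist.
- While editing, add one sentence on how sub-items are reduced to a single score of 0 to 1 per recommendation.

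The cost is a few sentences and one extra derived variable. No new data are needed, since the plan already provides for the measurements. The downside is one more score to report and explain.
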